### 1. Introduction

# 1.1. Study Rationale

Currently, no study has addressed real-life data describing changes in health resource consumption and related costs attributable to mepolizumab treatment. The aim of the current study is to fill this knowledge gap by performing an exhaustive extraction of data for patients receiving mepolizumab in the French single-payer health care system (via the national health data system or 'SNDS'). The change in real-life health-resource usage and costs observed for these patients would provide the first evidence that mepolizumab is changing the care landscape for eligible severe asthma patients.

### 1.2. Benefit/Risk Assessment

This study will be performed exclusively using French national claims database data (SNDS). As a non-interventional study based on secondary use of of medico-administrative data, it meets requirements for a 'European Network of Centers for Pharmacoepidemiology and Pharmacovigilance (EnCEPP) study'. Safety-relevant results will be presented as aggregated data only.

The reader should note that the current knowledge on mepolizumab indicates a list of quite minor side effects (injection site reactions, lower respiratory tract infections, urinary infections, pharyngitis, headache, back pain, and others as mentioned in the Summary of Product Characteristics). Compared with the long-term use of oral corticosteroids (OCS) or short acting beta antagonists (SABA) (currently the most-used anti-asthma medications)(Nwaru et al. 2020), whose side effects include adrenal insufficiency, diabetes, and increased mortality (Zazzali et al. 2015; Sweeney et al. 2016; Barry et al. 2017; Zeiger et al. 2017; Daugherty et al. 2018; Sullivan et al. 2018; Nwaru et al. 2020), mepolizumab initiation is hypothesized to not only decrease the costs associated with recurrent severe asthma, but also costs purportedly due to the comorbid burden associated with rescue medicine.

# 1.3. Limitations of the study design

Potential limitations of the study are related to the use of claims data, especially the completeness of prospectively accrued data and the paucity of clinical or biological data.

The SNDS provides clinical information about a specific disease only through coded discharge diagnoses and recorded Long Term Illnesses (ICD-10 codes), and the drug and medical devices used. The identification of patients with a certain disease or comorbidity often depends on the development of algorithms taking into account different combinations of hospital diagnoses or types of delivered drugs.

The SNDS does not provide paraclinical information and other risk factors such as smoking, weight, or body mass index (except when coded within hospitalization data). For the present study, no subgroup can be defined to assess mepolizumab exposure according to weight/bmi. However, age and sex subgroups can be defined. Drug related adverse events are not reported in the SNDS, so traditional safety analyses are not possible.

Mepolizumab exposure is based solely on its delivery; the actual exposure of the patient to the delivered drug is not measurable in this secondary database study, and this limitation should be mentioned in subsequent publications.

The overwhelming strength of the SNDS database is that it is one of the largest continuous countrywide claims databases. It covers just about the whole population (99%) essentially from birth to death, irrespective of the health care provider, age or socioeconomic status, and retirement status (Bezin et al. 2017). Patients keep the same identifier throughout their lifetime, and there are no restrictions in coverage related to income or social situation. At this point about 600 million patient years of data are stored, though not all are immediately accessible.

There are no risks to patients associated with study execution or study findings.

# 2. Objectives and Endpoints

In light of the clearly documented clinical efficacy of mepolizumab for the treatment of asthma, our hypothesis is that mepolizumab treatment results in decreased consumption of health care resources, with corresponding decreases in overall costs for the single payer social security health insurance program in France.

The overall objectives of this study are: (i) using the SNDS French national database, to identify a representative, nation-wide population of patients treated with mepolizumab with a follow-up period of at least 12 months, (ii) to describe the initial one-year changes in health resource use before and after the initiation of mepolizumab treatment and (iii) to estimate the change in associated costs for the first year of treatment. These initial data will additionally serve as a basis for the design of longer-term studies.

## Information available in the SNDS

The available **beneficiary characteristics** include date of birth, gender, area and region of residency, universal medical coverage status, and complementary health insurance status. Chronic diseases are classified according to ICD codes, with registration and end dates, if applicable. For deceased beneficiaries, the date of death is recorded, with the principal, related and associated causes of death.

**Inpatient care** is characterized via linkage with the PMSI database and comports the type of hospital (short-stay care, long-stay care and rehabilitation, psychiatry, or home-hospitalization), within-hospital trajectories (for example, passages through emergency departments or intensive care), principal and secondary diagnoses associated with hospital entry, the procedures performed during each stay, the consumption of a special drug category termed "costly drugs", entry and leave dates and associated mode (transfer, return home), and cost information.

**Outpatient care** comprises care not affected to a hospital stay and the related data include drug delivery (international non-proprietary name and anatomical therapeutic chemical classification, packaging identifier code, the common dispensing unit, quantity and date of delivery), medical devices (type, quantity and date of delivery), medical visits (date and speciality of the physician),

paramedical visits (date and type (nursing, physical therapy, etc)), medical procedures (date and type), lab tests (date and type), government benefits (beginning and end dates and type (disability, maternity, sick leave, etc), medical transportation usage. Each outpatient care element is further characterized according to professional source and legal status (pharmacy, specialist, nurse, therapist, etc), the area and region of residency, the price presented for reimbursement and the amount actually reimbursed by the single payer system.

### Describing the population

The index date "T0" is defined as the day upon which the beneficiary received a first dose of mepolizumab. Population characteristics will be tabulated at this time point and will include age, gender, area and region of residency, universal medical coverage status, and complementary health insurance status.

The population will be further described by providing the duration of treatment with mepolizumab (ie medication persistence (Cramer et al. 2008), defined as date of last administration – T0 in days) as well as the proportion of days of follow-up covered (PDC) by mepolizumab. The current authorized dosage for mepolizumab is a single 100 mg subcutaneous injection every 4 weeks (with an authorized leeway of +- 7 days), and the PDC will be determined accordingly.

## Drug consumption

All drug consumption will be analyzed, with specific attention given to (i) mepolizumab, (ii) corticosteroids (oral/IV/systemic, inhaled, topical, etc), asthma-specific medications (selective beta-2-adrenoreceptor agonists, adrenergics in combination with corticosteroids or other drugs, anticholinergics, adrenergics for systemic use, xanthines, leukotriene receptor antagonists, other systemic drugs for obstructive airway diseases, etc), and diabetes-related medications (buiguanides, insulin, etc). Drugs demonstrating significant changes in cumulative dose between the baseline and exposure periods (if any in addition to mepolizumab) will be identified.

#### **Hospitalizations**

The following will be compared between baseline and exposure periods: (i) the number of hospitalizations for asthma (the corresponding primary diagnosis ICD10 codes are Predominantly allergic asthma (J45.0), Nonallergic asthma (J45.1), Mixed asthma (J45.8), Asthma, unspecified (J45.9), and Status asthmaticus (J46)), (ii) the number of hospitalizations in general (all causes), (iii) the cumulative days of hospitalization (in association with asthma and for all causes), (iv) the cumulative days of intensive care (in association with asthma and for all causes). Each day of hospitalization can be considered as a recurrent event.

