#### **Consultations**

The cumulative numbers of consultations will be compared between the baseline and exposure period and differentiated according to type (general and specialist medical consults, nursing and other paramedical consults etc). Special attention will be given to pulmonology/allergology and metabolic/endocrine specialist consults, as well as nursing consults for injections.

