### 8.3.1.1. Mepolizumab exposure

Mepolizumab exposure will be characterized by cumulative numbers of injections and dosage.

Medication persistence is defined as the duration from T0 to the discontinuation of therapy (Cramer et al. 2008)(or the end of follow-up for the present study).

The proportion of days of follow-up covered (PDC) by mepolizumab (or the anologous medication possession ratio for dispensations) will also be calculated as the best available proxy for adherence and an important covariate for analyses or defining subgroups.

If mepolizumab is administered during a hospital stay, the dispensation might not be captured. This possibility will be explored by juxtaposing uncovered (non-PDC) time with hospital stays and investigating two extreme hypotheses: either all such stays contained the missing administration, versus no such stays contained the missing administration. This will provide minimum and maximum possible ranges for mepolizumab exposure.

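### Hospitalisation counts do not separate stays made to give mepolizumab, so any injections recorded as same-day stays could mask or reverse a fall in asthma admissions

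*Protocol*

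**What the plan says.** Protocol section 2, under Hospitalizations, lists the outcomes to be compared between the baseline and exposure years:

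- Asthma stays: "the number of hospitalizations for asthma (the corresponding primary diagnosis ICD10 codes are" J45.x and J46.
- All stays: "the number of hospitalizations in general (all causes").
- Days: "the cumulative days of hospitalization (in association with asthma and for all causes"), and likewise days of intensive care.

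No exclusion or separate category is given for stays whose purpose is to administer the study drug.

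Section 8.3.1.1 takes up in-stay administration: "If mepolizumab is administered during a hospital stay, the dispensation might not be captured". It then compares uncovered time with hospital stays under two extreme hypotheses. The stated purpose concerns exposure only: "This will provide minimum and maximum possible ranges for mepolizumab exposure".

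Elsewhere in section 2, injections also appear as an outpatient activity: under Consultations, special attention goes to certain specialist visits, "as well as nursing consults for injections". The inpatient data are said to include "the type of hospital (short-stay care, long-stay care and rehabilitation, psychiatry, or home-hospitalization"), and also "entry and leave dates and associated mode (transfer, return home), and cost information". Day-case or zero-night stays are not mentioned.

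**The concern.** The same event, a dose given within a hospital stay, is recognised on the exposure side and not carried to the outcome side. If some injection visits are recorded as stays, they enter the all-cause count whatever their coding, and the asthma count if their primary code is J45 or J46. T0 is the day of the first dose, so recognised injection stays cannot precede it. With an injection every 4 weeks they can recur throughout the exposure year. The before-after contrast would then mix drug delivery with admissions for disease, in the direction opposite to the hypothesised fall in resource use.

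The effect could spread. The indicator of uncontrolled asthma in section 2 uses hospitalisation for asthma, the cost levels there separate mepolizumab from asthma-specific care, and section 8.3.3 foresees mean cumulative functions for events found to differ.

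**Working it through.** **Inputs from the Protocol.** One injection every 4 weeks (section 2, Describing the population; used here only to count injections); 12 months on each side of T0 (section 3.1); 29 beneficiaries in a 1/97 sample, and at least 90% power for effect sizes above 0.063 (section 8.1); two-sided 5% level (section 8.3.1).

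**Assumptions, not in the documents.** The share *p* of injections recorded as same-day stays, full persistence over the year, the SD of the paired difference, the baseline admission rate and the true reduction. For the asthma count, *p* means the share recorded as same-day stays with a J45/J46 primary code.

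1. *The plan's own figures.* 29 × 97 = 2813. Power of a paired t-test (noncentral t, two-sided 0.05, d = 0.063, n = 2813) is 0.916. For the Wilcoxon test, with effective n = n × 3/π, it is 0.904. Both agree with the stated 90% or better and are not in dispute.

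2. *Injections in the exposure year.* Days 0, 28, ..., 364 give 364/28 + 1 = 14, or 13 without the T0 dose.

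3. *Extra stays per patient* = *p* × 13 to *p* × 14:

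| *p* | extra stays per patient-year |
|---|---|
| 0% | 0 |
| 1% | 0.13-0.14 |
| 5% | 0.65-0.70 |
| 10% | 1.3-1.4 |
| 100% | 13-14 |

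4. *Against the plan's detectable effect.* An effect size of 0.063 equals 0.063 × SD stays. For an SD of 1, 2, 3 or 5 that is 0.063, 0.126, 0.189 or 0.315 stays. Dividing by 14 gives *p* = 0.45%, 0.9%, 1.35% or 2.25%. These shares hold the SD fixed, so they are lower limits. If the stays are concentrated in a few patients, the SD grows too. For example, if 0.45% of patients have all 14 injections as stays, independently of their other stays, the added variance is 14² × 0.0045 × 0.9955 = 0.878. An SD of 1 becomes √1.878 = 1.37, and the standardised shift is 0.063/1.37 = 0.046.

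5. *Share that cancels a true fall* = baseline rate × reduction / 14 (or / 13). With a reduction of 50%:

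| baseline stays per year | share that cancels |
|---|---|
| 0.5 | 0.25/14 = 1.8% to 0.25/13 = 1.9% |
| 1 | 0.5/14 = 3.6% to 0.5/13 = 3.8% |
| 2 | 1/14 = 7.1% to 1/13 = 7.7% |

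6. *Days.* A same-day stay adds no day if days are leave date minus entry date, and one day if calendar days are counted. The Protocol does not say which, so the effect on days lies between zero and the figures in step 3.

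**The case against.** The strongest reply is that the premise is not in the Protocol. Nothing there says that an injection visit is recorded as a hospital stay. Section 8.3.1.1 is conditional, and it can be read as a dose that fell due while the patient was already admitted for another reason, which adds no admission. Nursing consults for injections are expected outside hospital. A reader might infer that injection visits *will* be counted as admissions; the documents support only that they *could* be.

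Four further points have weight:

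- The cohort is anchored on a first filled prescription and found by medication codes. Patients treated only within stays may therefore never enter it, which limits the plausible share.
- It is tempting to say that such stays fall in the exposure year only. That is not secure: an uncaptured first dose would place T0 too late and put an injection stay in the baseline year.
- For the all-cause count, a stay to deliver the drug is genuine resource use, which is what the study sets out to measure. Removing it would understate consumption in the exposure year.
- How same-day stays are handled is often left to an analysis plan, which is not shown.

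These points limit the claim without removing it. The Protocol itself defines the outcome, down to the ICD-10 codes, and foresees in-stay administration without saying what this means for the counts. Section 8.3.1.1 does not confine itself to stays made for another reason. For asthma admissions, read as a sign of disease control, the mixture would matter.

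**Conclusion.** The point holds as a conditional weakness of secondary outcomes. As written, the hospitalisation counts cannot tell treatment delivery from admissions for asthma, and any injection stays would fall almost entirely on one side of the comparison. Each 1% of injections recorded as same-day stays adds about 0.13-0.14 stays per fully persistent patient-year. Under the assumed baseline rates of 0.5 to 2 stays and a true halving, a share of about 1.8% to 7.7% would cancel the fall, and a larger share would reverse it.

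A reader might go on to infer that the reported change will have the wrong sign. The documents do not support that: the share, the baseline rate, the coding of such stays and full persistence are all assumptions, and the share may be zero. Nor is the primary endpoint at fault, since the cost of an injection stay belongs in total cost.

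**What to change.** In Protocol section 2, Hospitalizations:

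- Split stays in both periods into overnight and same-day (entry date equals leave date). Report asthma and all-cause counts and days both with and without same-day stays.
- Where a mepolizumab administration is recorded in a same-day stay, or the stay matches a coverage gap in the section 8.3.1.1 check, show it as a separate treatment-delivery category.
- Keep the all-cause total, with all stays, as the resource-use measure. Use the version without same-day stays to interpret the change in asthma admissions.

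Two stronger remedies should be avoided. Redefining hospitalisation as overnight stays alone would drop genuine same-day asthma admissions from the outcome. Charging same-day stays to treatment because they fall near an expected injection date would be too loose: with the 7-day leeway either way, the window covers 15 of every 28 days (15/28 = 54%).

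The cost is one extra tabulation, using dates that the Protocol lists as available. Genuine same-day asthma admissions are absent from the overnight version but remain visible in the total.

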#### **Consultations**

The cumulative numbers of consultations will be compared between the baseline and exposure period and differentiated according to type (general and specialist medical consults, nursing and other paramedical consults etc). Special attention will be given to pulmonology/allergology and metabolic/endocrine specialist consults, as well as nursing consults for injections.

### Assessments/procedures

Information concerning the laboratory and imaging assessments performed is available, but not their results. Special attention will be given to lung function, adrenal function, glycemia, and bone

density assessments. The cumulative numbers of different assessments will be described and contrasted between the baseline and exposure periods.

### Diagnoses / Comorbidities

Resource-use algorithms will be developed as indicators of severe asthma (via a combination of specific asthma controllers and oral corticosteroids), uncontrolled asthma (combinations of oral corticosteroids, hospitalization for asthma, specialist and/or emergency care usage), chronic obstructive pulmonary disease and diabetes (specific drug deliveries). Evidence of further comorbidities will be collected (via a specific list of long-term diseases, and via the primary and secondary coding performed during hospitalizations) and their incidence before versus after T0 studied.

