### Subpopulations of interest

Sub populations of interest and subject to comparative analyses include sex, age groups, beneficiaries with versus without indicators of severe asthma, uncontrolled asthma, chronic obstructive pulmonary disease, and diabetes (identified via the prescription of specific drugs, hospitalization diagnoses, assessments or combinations thereof).

Objectives	Endpoints
Primary	
To estimate the change in associated costs for the first year of treatment	
 
Total health care costs for the year preceding the initiation of mepolizumab, as well as for the year after.
 

Secondary	
To describe the initial one-year changes in health resource use before and after the initiation of mepolizumab treatment	
 
Cumulative estimates for health resource use and associated costs for the year preceding the initiation of mepolizumab, as well as for the year after.
 

Tertiary/Exploratory	
To further characterize rates of change in health resource usage and/or costs in subpopulations of interest	
 
Sub populations of interest and subject to comparative analyses include sex, age groups, beneficiaries with versus without indicators of severe asthma, uncontrolled asthma, chronic obstructive pulmonary disease, and diabetes (identified via the prescription of specific drugs or combinations thereof).
 

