# 3. Study Design

## 3.1. Overall Design

This retrospective, non-interventional (not involving human subjects) database study will compare real-life patient health resource consumption before versus after a first injection of mepolizumab. Data concerning patients receiving mepolizumab will be collated for a 12-month period (the "baseline period") preceding a first index treatment (at "T0") and compared to a 12-month period occurring after the index treatment (the "exposure period")(Figure 5-1).

[figure not shown]

Figure 3-1 Graphic presentation of the basic study design comparing health care resource use data between a one-year baseline period and a one-year exposure period after the first administration of mepolizumab (T0).

The expected correspondence to calendar time (Figure 5-2) is an inclusion period for T0 starting in February 2018 to December 2018, with 12 months of "follow-up" corresponding to the year 2019. It follows that baseline data will reach back to February 2017. If data for exposure periods longer than 12 months are available, these will also be collected to describe future trajectories of health resource use in as much as possible.

Figure 3-2 The expected correspondence with real time is an inclusion period covering patients who started mepolizumab in the year 2018, with 12 months of "follow-up" in the year 2019.

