#### 8. Statistical Considerations

# **8.1.** Sample Size Determination

This study is primarily descriptive and the identification of beneficiaries receiving mepolizumab in the SNDS will be exhaustive. In this context, traditional sample size calculations are not appropriate/unnecessary.

A first, preliminary analysis of the EGB, a 1/97th random permanent sample of the SNIIRAM French national database (Bezin et al. 2017), currently yields 29 beneficiaries having received mepolizumab during the 11 month period starting in February 2018 and ending in December 2018. We therefore aim to analyze data for approximately  $29 \times 97 = 2813$  beneficiaries receiving mepolizumab with 1 year of follow-up time.

Considering a type I error rate of 5% ( $\alpha$ =0.05), a sample size of 2813 yields *a posteriori* power estimates of 90% or better for cohen's effect sizes superior to 0.063 (Figure 10-1). The latter indicates ample power to detect very small effects (an effect size of 0.2 is considered as "small").

[figure not shown]

Figure 8-1 Effect size versus power for paired t-tests or for paired Wilcoxon tests (non-parametric option) when the type 1 error rate is set at alpha=0.05 and a sample size of 3000 is expected.

NB: This preliminary sample size analysis also served as a testing ground for the primary patient-selection algorithm (based on medication codes UCD 9413850 // code CIP\_C13 3400930038352), which is now finalized.

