# 8.3. Statistical Analyses

### **8.3.1.** General considerations

Children and adult patient data will be analyzed (no age limits will be imposed).

Descriptive statistics for quantitative variables will include sample size and number of missing values, range, median (interquartile range), and mean ± standard deviation. Summary statistics for qualitative variables will include sample size and number of missing values, the frequency and percentage (over non-missing values unless otherwise specified) for each category. All applicable statistical tests will be performed using a bilateral 5% significance level. All confidence intervals (CI) presented will be 95% and two-sided.

The lost to follow-up patients (e.g. exit from one of the insurance schemes available in the SNDS, expatriation with exit from French insurance schemes) will not be included in the study. No replacement of missing values will be performed. For a given patient with a complete follow-up period, all reimbursed healthcare consumptions are reported in the database.

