#### 8.3.2. Comparing health resource usage and costs before and after T0

Descriptive statistics for the different types of health resource usage and their associated costs will be calculated for both the baseline and exposure periods. Differences between the two study periods will be presented with their 95% confidence intervals. Statistical techniques for paired data (paired t-tests, paired Wilcoxon tests) will be used to compare variables between the two periods. Potential covariates/subgroups-of-interest will be tested via interaction terms (covariate x period interactions) in mixed models with patients as fixed effects or via regression models explaining the change in resource use ( $\Delta$ baseline period-exposure period). Due to the descriptive and exploratory nature of this study, results will be presented with and without the application of a False Discovery Rate (FDR) correction for multiple testing.

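### The severe- and uncontrolled-asthma subgroups are built from resource use that is also an outcome, so a subgroup-by-period interaction cannot be read as a differential treatment effect

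*Protocol*

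**What the plan says.** Section 2 (Diagnoses / Comorbidities) defines the uncontrolled-asthma indicator as "uncontrolled asthma (combinations of oral corticosteroids, hospitalization for asthma, specialist and/or emergency care usage". The severe-asthma indicator combines asthma controllers with oral corticosteroids. Neither has a stated time window.

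Other parts of section 2 make the same items outcomes to be compared between periods: corticosteroids and asthma drugs (Drug consumption), asthma admissions (Hospitalizations) and specialist visits (Consultations). All of them feed the Costs paragraph.

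Section 2 (Subpopulations of interest) names "beneficiaries with versus without indicators of severe asthma, uncontrolled asthma" among the groups to be compared, and the objectives table places this under the tertiary/exploratory objective on rates of change. Section 8.3.1.3 applies the primary-endpoint strategy to subgroups. Section 8.3.2 adds: "Potential covariates/subgroups-of-interest will be tested via interaction terms (covariate x period interactions", in mixed models with a fixed effect per patient, or alternatively by regression on the change.

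Section 3.1 sets a 12-month baseline, "compared to a 12-month period occurring after the index treatment". T0 runs from February to December 2018, and baseline data start in February 2017.

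**The concern.** If the indicator is read in the baseline year, it is partly a function of the baseline value of the outcome. Patients flagged because that year was bad will on average have a less extreme next year, and unflagged patients will move the other way relative to them. The difference in change between the two groups is then non-zero without any drug effect. This is separate from regression to the mean in the whole cohort, because here the artefact lies in the contrast between subgroups.

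The planned analysis does not remove it. With two periods per patient, a patient fixed effect reduces the interaction to a comparison of change scores, which is exactly the biased quantity. A false discovery rate correction addresses the number of tests, not bias in each one. There is no untreated comparison group. At stake is a report that patients with uncontrolled asthma gain most, when the pattern may come from how they were selected.

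**Working it through.** **Inputs from the protocol.** Section 8.3.1: "All applicable statistical tests will be performed using a bilateral 5% significance level". Section 8.1: the sample "currently yields 29 beneficiaries having received mepolizumab during the 11 month period", hence 29 × 97 = 2,813. **Assumed, not in the documents:** year-to-year correlation ρ of 0.3 to 0.9, subgroup share q of 20% to 70%, and the event rates in step 5.

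**1. The plan's own figure.** Section 8.1 claims "power estimates of 90% or better for cohen's effect sizes superior to 0.063". The normal approximation gives Φ(0.063 × √2813 − 1.960) = Φ(3.341 − 1.960) = 91.6%. For the paired Wilcoxon test, multiplying n by 3/π gives 90.4%. The claim is reproduced. The figure caption says "a sample size of 3000 is expected", at which the t-test power would be 93.2%; this makes no difference here. These powers are for the whole-cohort paired comparison, and only N and alpha carry over.

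**2. Which window do the data allow?** A patient starting in February 2018 has no data before the baseline year. A patient starting in December 2018 has about 10 months (February to December 2017). No patient has a separate full year before baseline.

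**3. Null interaction when indicator and outcome coincide.** Take standardised baseline and exposure years with correlation ρ, no treatment or period effect, and flag the top share q on the baseline value, with cut-point k. The expected difference in change (flagged minus unflagged) is

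−(1 − ρ) × [φ(k)/q + φ(k)/(1 − q)] single-year SDs.

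For a median split the bracket is 4 × 0.3989 = 1.596.

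| ρ | Median split | Range over q = 20% to 70% |
|---|---|---|
| 0.3 | 0.7 × 1.596 = 1.12 | 1.12 to 1.23 |
| 0.5 | 0.5 × 1.596 = 0.80 | 0.80 to 0.88 |
| 0.7 | 0.3 × 1.596 = 0.48 | 0.48 to 0.53 |
| 0.9 | 0.1 × 1.596 = 0.16 | 0.16 to 0.18 |

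In simulation (N = 2,813, 1,000 runs per setting, shares 30% and 50%, Welch test of the change), 100% of runs were significant at every ρ. Even at ρ = 0.9 the SE for a median split is about 2 × √(2 × 0.1)/√2813 = 0.017, against a gap of 0.16. Cutting on the exposure year gives the same sizes with the opposite sign, by symmetry.

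**4. Partial overlap.** If the indicator correlates c with the baseline outcome, only through that year's value, the gap is multiplied by c.
- c = 0.3: 0.05 to 0.35 SD, significant in 79% to 100% of runs.
- c = 0.1: 0.02 to 0.12 SD, significant in 14% to 71% of runs.

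**5. Count example.** Let patient rates be gamma with mean 0.5 per year and shape 0.5 (scale 1), with Poisson events and no effect. Flag patients with at least one baseline event.
- P(no event) = 2^(−0.5) = 0.707.
- Unflagged: 0 at baseline, then 0.5/2 = 0.25.
- Flagged: 0.5/0.293 = 1.71 at baseline, then (0.5 − 0.707 × 0.25)/0.293 = 1.10.

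Flagged patients fall by about 0.60 and the others rise by 0.25. All 500 simulated runs were significant.

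**6. Does an earlier year cure it?** With equal correlation between all years, an indicator from a separate earlier year gives 4.1% to 6.8% false positives. If correlation decays as AR(1), the earlier year correlates ρ² with exposure and ρ with baseline, so a median split leaves a gap of ρ(1 − ρ) × 1.596: 0.34, 0.40, 0.34 and 0.14 SD at ρ = 0.3, 0.5, 0.7 and 0.9. A symmetric two-year indicator gives 3.9% to 5.9% in the null model, but it classifies patients partly on post-treatment use.

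**The case against.** The strongest reply is that the protocol never says the indicators are read at baseline. It says only that algorithms will be developed, and a window can be left to the statistical analysis plan. A reader might infer that a baseline window is written down; it is not. What remains is that an analysis plan can choose only from data that were extracted, and the Data Management appendix requires the selection algorithm and variable list in advance. Within the planned range, either one-sided choice, baseline or exposure year, biases the contrast.

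Second, section 8.3.4 lists age, sex, a grouping by change in medication use, COPD and diabetes, but not severe or uncontrolled asthma. That weakens the link to the interaction test without breaking it: the list is introduced as what the subgroups include, and section 2 names both indicators explicitly.

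Third, a reader might infer a large artefact in every comparison. The documents do not support that. The 100% rejection rate applies where indicator and outcome nearly coincide. The indicators are combinations of items, and many outcomes (all-cause care, diabetes care, total cost) overlap only in part. If controller and corticosteroid use is stable between years, the severe-asthma gap may be small.

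Fourth, it is tempting to say that the ranking of subgroups is fixed whatever the drug does and that low users must rise. Only a stationary no-effect model was examined. With a real or cohort-wide fall, low users need not rise.

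**Conclusion.** The concern holds in conditional form. The subgroup indicators share components with the outcomes, no window is fixed, and nothing in the design or analysis controls regression to the mean between subgroups. If the baseline year is used, as the data range makes likely, a null interaction is expected. It is about 1.1 to 0.5 SD for a median split at ρ of 0.3 to 0.7 when indicator and outcome coincide, 0.16 to 0.18 SD at ρ = 0.9, and less with weak overlap. It is best supported for the uncontrolled-asthma subgroup and for oral corticosteroids, asthma admissions and specialist care. All correlations, shares and event rates are assumptions.

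A reader might extend this to the headline result. That is not supported: the primary whole-cohort cost comparison does not use these subgroups, and the affected objective is tertiary/exploratory.

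**What to change.** In sections 2, 8.3.2 and 8.3.4:

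- State the window over which the severe- and uncontrolled-asthma indicators are measured, and make the subgroup list in 8.3.4 agree with section 2.
- For any resource or cost component that enters an indicator, do not test the indicator-by-period interaction. Report the subgroup changes descriptively, and state that they cannot be read as differential treatment effects.
- Attach the same caution to total cost and other partly overlapping outcomes.
- If the extraction can be extended, add a sensitivity analysis with the indicator taken from T0−24 to T0−12 months. Say that this reduces the artefact but does not remove it if year-to-year correlation decays with time.

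The text changes cost a few sentences and some formal subgroup tests. The sensitivity analysis needs one more look-back year, to February 2016, and loses patients without that history. Section 1.3 notes that not all stored data are immediately accessible, so feasibility should be confirmed before the extraction is specified.
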